The overall purpose of this protocol is to assess the biomechanical and neurophysiologic effects of rehabilitative strategies and protocols that are commonly used during physical therapy treatment of gait disorders post-stroke. As part of this protocol, 45 able-bodied individuals and 55 individuals with chronic stroke will be assigned to either Cohort 1 or Cohort 2, and will participate in 1-18 gait training sessions. If interested, study participants can also complete both study cohorts sequentially (with at least 3-weeks duration between switching from one cohort to the second). Evaluations for obtaining outcome measures will comprise clinical testing, muscle evaluations, gait analysis, and assessment of spinal and corticospinal excitability. Within Cohort 1 (stroke and able-bodied), 25 subjects will receive identical treatment throughout the training sessions (i.e. FastFES training). Within Cohort 2, 25 subjects will receive different rehabilitation strategies individually or in combination during each training session (e.g., treadmill walking, functional electrical stimulation, bio-feedback or verbal feedback about targeted walking parameters, split-belt walking, etc.). During gait training, Cohort 1 subjects will typically participate in a minimum of 2 and a maximum of 3 sessions per week. Subjects in Cohort 2 can participate in 1 to 18 gait training sessions but the frequency of the gait sessions can be varied according to the subject's and laboratory schedule (i.e. variable durations between consecutive sessions).

Aims

The aims of this protocol are to:

- 1) Study the changes in gait biomechanics, corticospinal excitability, and walking function during 18 sessions of gait retraining (Cohort 1).
- 2) Systematically determine the effect of parameters such as walking speed (slow, fast, variable, split-belt walking), functional electrical stimulation parameters (short-term changes induced by fast versus FastFES, stimulation intensity, number of muscles stimulated), and bio-

[figure not shown]
feedback on within-session changes in gait biomechanics, walking function, and corticospinal excitability (Cohort 2).

Hypotheses of the study

- By utilizing data collected on cohort 1 of subjects who undergo 18 sessions of FastFES gait retraining, the following hypothesis will be tested:

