during these testing procedures, rest breaks will be provided to the subjects as needed and as requested by the subject. Please see the adjoining flowchart for a summary of the procedures that subjects in each study cohort will undergo. Subjects will not be randomized to the 2 cohorts. Assignment to the cohorts will be based on the lab/personnel and subject schedules. A subject can participate in the 2 cohorts sequentially. Also, participants in Cohort 2, when testing hypotheses comprising a repeated-measures comparison of different gait training strategies (e.g. Hypothesis 4a evaluating effect of walking speed; Hypothesis 4b comparing FastFES versus Fast), participants may cross-over between strategies within or across gait sessions.

1) Medical Clearance:

If a subject shows interest in participation in cohort 2 of the study (18 training sessions), before participation, we will obtain written medical clearance from the subject's physician (See attached Medical Clearance form). In addition, the subject will undergo clinical assessment to confirm that they are eligible for study participation.

2) Procedures for Clinical Assessment of Walking Function and Muscle Strength:

All subjects will review and sign consent forms before clinical testing. Clinical Testing will be performed by a licensed physical therapist. Clinical testing may comprise: (1) measurement of subjects' over ground self-selected (SS) walking speed (6-meter walk test); (2) over ground walking endurance measured by the distance ambulated during the 6-minute walk test; (3) assessment of gait and dynamic balance (measured using the functional gait assessment, 4-square step test, and the Berg balance score); (4) lower extremity portion of the Fugl-Meyer score⁷⁰; (5) step activity monitoring; (6) lower extremity proprioception (in which each limb segment will be flexed or extended approximately 10 degrees and the subject will be asked to identify whether the limb is moving and in what

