direction); (7) Lower extremity sensation utilizing monofilaments. Each limb segment will be tested and the smallest diameter filament that can be felt reliably (4 out 5 trials) will be recorded. Additional clinical measures may include measures of cognitive impairments and self-reports (e.g. Stroke Impact Scale, Walk-12 questionnaire, Activity-specific Balance Confidence Scale, reports of physical activity levels). These measurements will provide an assessment of the severity of subject impairments. In addition, the subject's fast walking speed will be determined as the fastest speed the subject can attain during a 4-minute bout of treadmill walking. For able-bodied subjects, the clinical testing may not be performed or may only comprise a subset of the outcomes listed above.

In addition, during this session, after completion of clinical testing, **assessment of muscle strength** may be performed using procedures described below.

Muscle strength of the subjects' bilateral knee extensor, knee flexor, ankle plantarflexor, and ankle dorsiflexor muscle groups will be evaluated.

Positioning for Measurement of Knee Strength: For evaluating the knee muscles, the subject will be seated on a force dynamometer with the hips and knees bent at approximately 90 degrees. The subject's leg will be strapped to the arm of the dynamometer. In addition, inelastic belts will be used to strap the subject's trunk and thigh to the dynamometer chair for stabilization. The subject will be asked to 'kick out' (for knee extensors) or 'pull in' (for the knee flexors) with the leg being tested with as much force as possible.

Positioning for Measurement of Ankle Strength: For evaluating the ankle muscles, the subject will be positioned supine on the force dynamometer with the hips and knees extended, and the foot strapped to the dynamometer arm. The shank, thigh, and trunk will be stabilized using inelastic straps. The subject will be asked to 'pull the foot in' (for the ankle dorsiflexors) or 'push the foot down' (for the ankle plantarflexors) with as much force as possible.

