Burst superimposition during muscle strength testing: A technique called the burst superimposition technique will be used for measurement of the subject's muscle strength. This technique has been used to safely obtain a quick and accurate measurement of muscle strength in young and elderly able-bodied individuals as well as patient populations⁷¹⁻⁷³. For this technique, while the subjects are generating their maximal contraction force volitionally, a supra-maximal burst of electrical stimulation (100-Hz frequency, 100-ms duration, 600 μ s pulse duration) will be delivered to the muscle. The force generated by the muscles will be recorded via a force dynamometer. The 'true' force generating ability of the muscle will be calculated as the total force generated by the subject's volitional contraction and the superimposed electrical stimulation. The maximal contraction will be repeated 2 times for each leg.

3) **Cardiac Exercise Stress Test:**

After confirming the subject's eligibility for participation in the study and clinical testing, if the subject is part of Cohort 1 that will participate in the intensive 18-sessions of gait training, the subject will be referred for a cardiac exercise stress test (treadmill exercise test). The exercise stress test will be conducted under the supervision of a cardiologist at Emory University (referral will be provided as part of this research protocol). The stress test will help confirm that the subjects who participate in the intensive gait training

treatment sessions have sufficient cardiovascular health to participate in a treadmill exercise intervention. If a participant is unable to complete the stress test due to musculoskeletal impairments or other factors unrelated to cardiac health (e.g. muscle weakness, ankle instability, inability to walk at sufficiently fast speed or incline due to post-stroke muscle weakness), then the tolerance and appropriate dosage for treadmill training will be determined based on consultation with the cardiologist, exercise physiologist, and physical therapists.

4) Procedures for Gait Training Sessions:

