
Procedures for MRI Scans (for a subset of 15 able-bodied individuals):

As stated above, the MRI scans will be obtained as part of a different IRB protocol. The IRB

protocols that we are requesting permission to use the brain MRI scans from are two protocols whose PI ([name]) is a co-investigator in the current IRB protocol: IRB00081268 (Noninvasive brain stimulation to evaluate neural plasticity after stroke) and IRB00072542 (Using concurrent brain imaging and stimulation to characterize brain behavior in stroke). The methods for the MRI will be as described in the above protocols, and for convenience are also listed here.

MRI acquisition: Scanning will be conducted at Emory University at the Center for Systems Imaging on a Siemens 3T Trio whole-body MRI scanner. A high-resolution T₁ scan (TR = 7.4ms, TE = 3.7ms, flip angle θ = 6°, FOV = 256mm, 160 slices, 1 mm thickness, scan time=3.2min) will be performed without contrast. The study team will have direct and immediate access to the data using Emory University's secure network server.

Risks

Risks associated with clinical testing, gait training, and motion analyses include falling, fatigue, poor heart rate and blood pressure response to walking and minor skin irritation from the adhesive tape. To minimize risk, subjects will wear a safety harness during the treadmill testing and will be given a rest break whenever requested. Heart rate will be monitored continuously and blood pressure will be monitored at rest breaks. If heart rate exceeds 80% of their age predicted heart rate maximum, walking will be stopped until it returns to baseline. If a subject's blood pressure exceeds 190/100 mmHg, the session will be stopped and their blood pressure will be continually monitored until it returns to baseline. The subject's primary or referring physician will be notified. Throughout the experiment, the experimenter has access to an emergency safety switch that can be used to stop the treadmill immediately. To ensure sufficient cardiovascular health to complete an intensive gait training program, stroke subjects who participate in 18 sessions of gait training (Cohort 1) will complete a cardiac exercise stress test.

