Subjects will not be anonymous to the researchers. As a first step during data management, subject identities will be de-identified by assigning each subject a number. Any computer files containing information that link the identifiable subject data with the de-identified subject number will be password protected and stored on a secure Emory University computer. Only de-identified data will be used to compile spreadsheets of the various outcome measures collected as part of this study (joint angles, clinical impairment scores, EMG, etc.). De-identified data may be stored for future use until 5-years after completion of the study. All signed consent forms will be stored in the subject's folder (organized by de-identified subject numbers) in a locked file cabinet at the University. Participants will not be audiotaped, photographed or videotaped without their permission during this study.

6. Participant selection

We plan to collect data on a sample of 55 individuals post-stroke and 35 able-bodied individuals. However, we anticipate a withdrawal rate of ~10%. Therefore, we will recruit 60 subjects and 45 able-bodied subjects.

Inclusion Criteria for Post-Stroke Subjects are: 1) age 30-80 years, 2) chronic stroke (>6 months post stroke), 3) first (single) lesion, 4) ambulatory with or without the use of a cane or walker, 5) sufficient cardiovascular health and ankle stability to walk for 6 minutes at their self-selected speed without an orthoses, 6) resting heart rate 40-100 beats per minute, 7) resting blood pressure between 90/60-70/90.

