Exclusion Criteria for Post-Stroke Subjects are: 1) evidence of moderate/ severe chronic white matter disease or cerebellar stroke on MRI, 2) cerebellar signs (ataxic ("drunken") gait or decreased coordination during rapid alternating hand or foot movements, 3) insulin dependent diabetes, 4) history of lower extremity joint replacement, 5) score of >1 on question 1b and >0 on question 1c on NIH Stroke Scale, 6) inability to communicate with investigators, 7) neglect/hemianopia, or unexplained dizziness in last 6 months, 8) neurologic conditions other than stroke, 9) orthopedic problems in the lower limbs or spine (or other medical conditions) that limit walking. Additional exclusion criteria for TMS (measurement of corticospinal excitability) are: 10) history of seizures, 11) metal implants in the head or face, 12) history of recurring or severe headaches/migraine, 13) headache within the past 24 hours, 14) presence of skull abnormalities or fractures, 15) hemorrhagic stroke, 16) history of dizziness, syncope, nausea, or loss of consciousness in the past 12 months.

Inclusion Criteria for Able-Bodied Individuals are: 1) age 21 to 80 years, 2) no history of neurologic disease, 3) no history of orthopedic disease or injury affecting the lower extremity.

Exclusion Criteria for Able-Bodied Individuals are: 1) history of neurologic disease, 2) history of orthopedic disease or injury to the lower extremity, 3) an implanted cardiac pacemaker. Additional exclusion criteria for the TMS portion of the study (corticospinal excitability measurement) are: 4) history of seizures, 5) metal implants in the head or face, 6) history of recurring or severe headaches/migraine, 7) headache within the past 24 hours, 8) presence of skull abnormalities or fractures.

Subject Recruitment. Study participants will be recruited from the general community within and outside Emory University.

Withdrawal from study. Participation in the present study will be voluntary and subjects will be able to opt out of the study at any time.

Our subject population will be representative of adult patients with stroke and healthy adults. The incidence of stroke is considered rare in children, estimated to be less than 13 cases per 100,000 children⁸⁸ and their inclusion would not provide additional information compared with the data gathered in adults.

7. Statistical analysis

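### Section 5 leaves unclear whether able-bodied Cohort 1 trainees get the cardiac stress test: procedure 3 covers the whole cohort, while the Risks text names stroke subjects

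*Combined protocol and SAP*

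**What the plan says.** **Stress test.** Section 5, procedure 3 (Cardiac Exercise Stress Test) makes cohort membership the trigger for referral: "After confirming the subject's eligibility for participation in the study and clinical testing, if the subject is part of Cohort 1". The Risks text, also in Section 5, says that "stroke subjects who participate in 18 sessions of gait training (Cohort 1) will complete a cardiac exercise stress test".

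**Who is in Cohort 1.** Section 4 (Objectives): "Within Cohort 1 (stroke and able-bodied), 25 subjects will receive identical treatment throughout the training sessions". That treatment is FastFES. Procedure 4 describes 18 sessions of up to six 6-minute bouts, the last of which may be overground walking at the subject's fastest pace.

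**Entry criteria (Section 6).** Stroke participants need "sufficient cardiovascular health and ankle stability to walk for 6 minutes at their self-selected speed", and must also meet a resting heart rate range and a resting blood pressure range. For able-bodied people the list opens "Inclusion Criteria for Able-Bodied Individuals are: 1) age 21 to 80 years, 2) no history of neurologic disease" and adds an orthopedic item. Their exclusions repeat these items and add an implanted pacemaker, with further items for the brain-stimulation part only.

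**Other safeguards.** Procedure 1 (Medical Clearance) requires written clearance from a physician before participation, but attaches it to Cohort 2 while describing that cohort as the one with 18 training sessions. Procedure 4 introduces heart rate monitoring during training for stroke survivors; the Risks text states it without that limit.

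**Order of procedures.** Procedure 1 says that "the subject will undergo clinical assessment to confirm that they are eligible for study participation". Procedure 2, the clinical assessment, includes a treadmill test in which "the subject's fast walking speed will be determined as the fastest speed the subject can attain during a 4-minute bout of treadmill walking".

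**The concern.** Someone running the study has to know whether an able-bodied volunteer for Cohort 1 goes for the stress test, and the two passages that assign it describe different groups. Both justify the test by the demands of the training programme. Under Section 4 that programme is identical for everyone in Cohort 1, so the stated reason does not explain why one passage names only part of the cohort.

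What is at stake is participant safety and uniform conduct. If staff work from the Risks text, an able-bodied person of up to 80 could begin an intensive treadmill programme without the stress test, having met no entry criterion on fitness, resting heart rate or blood pressure. If they work from procedure 3, the same person would be tested.

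**Working it through.** No formula applies and the plan gives no figure to reproduce. The check sets the passages side by side.

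| Safeguard | Wider reading | Narrower reading |
|---|---|---|
| Stress test | Procedure 3: any Cohort 1 subject | Risks: stroke subjects in Cohort 1 |
| Physician clearance | Procedure 1, by session count: the 18-session programme, stroke or not | Procedure 1, by label: Cohort 2 |
| Heart rate monitoring in training | Risks: no restriction | Procedure 4: stroke survivors |

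1. **Does the stress test reach able-bodied trainees?** Under procedure 3, yes. Under the Risks text they are not mentioned. Procedure 3 itself seems to have been drafted with stroke in mind, since its examples of why someone might fail to complete the test include weakness after stroke.

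2. **Do the entry criteria fill the gap?** Stroke entry has three cardiovascular items (inclusion criteria 5, 6 and 7). The able-bodied list has none of these three kinds. Its one cardiac item is the pacemaker exclusion, which does not assess fitness for treadmill training.

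3. **Does physician clearance fill the gap?** Not reliably. The Precis, the Aims and procedures 3 and 4 make the 18-session FastFES programme Cohort 1, which suggests that the label in procedure 1 is a slip. But Section 4 lets Cohort 2 have 1 to 18 sessions, and procedure 4 also speaks of 18 sessions for Cohort 2. The session count therefore does not prove that Cohort 1 was meant.

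4. **Does monitoring fill the gap?** Procedure 4 and Risks differ on whether heart rate monitoring covers able-bodied people. In either case, monitoring acts during a session and does not replace a test done before training starts.

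5. **How many people?** Cohort 1 is planned at 25. The split between stroke and able-bodied is not given. If at least one of the 25 has had a stroke, at most 25 − 1 = 24 are able-bodied; the lower limit is 0. Section 7 powers the study on propulsive force of the paretic leg, which only stroke participants have, so a small number or none is plausible.

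6. **Order.** Eligibility is confirmed through the clinical assessment, the fastest-speed bout belongs to that assessment, and referral for the stress test follows it. As written, the 4-minute bout comes before the stress test. Able-bodied clinical testing may be reduced or omitted under procedure 2, so this bears mainly on stroke participants.

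**The case against.** The strongest reply is that nothing here is a flat contradiction. The Risks sentence says that stroke subjects in Cohort 1 will have the test; it does not say that others will not. Referring everyone in Cohort 1 satisfies both passages. The overview in Section 5 also speaks of young able-bodied people. The flowchart of procedures by cohort, which is not available in the text reviewed, might settle who gets what. These points stand. They make the matter an ambiguity of scope, but they do not remove it: a reader of the Risks text alone would not refer an able-bodied trainee, and the age limit in Section 6 is 80.

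A reader might go further and infer that the order of procedures defeats the purpose of the stress test, so that stroke participants do strenuous walking unscreened. The documents do not support that. Procedure 3 ties the test to the intensive training intervention and places it before that training, which fits its stated purpose. Before the bout, stroke participants are subject to entry criteria on cardiovascular health, heart rate and blood pressure. The Risks text covers clinical testing with monitoring and stopping limits (80% of age-predicted maximum heart rate; 190/100 mmHg).

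A reader might also infer that able-bodied people face no cardiac entry criterion at all. The pacemaker exclusion shows otherwise.

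**Conclusion.** The point holds as an inconsistency of scope. Procedure 3 and the Risks text do not name the same participants for the stress test, and the clearance and monitoring passages carry similar uncertainties of their own. An able-bodied Cohort 1 trainee could start 18 sessions without the stress test only if the Risks wording is taken to govern. For that person also to lack physician clearance, procedure 1 must in addition be read by its cohort label. The conclusion further assumes that able-bodied people really do the Cohort 1 training, as Section 4 says.

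The number affected cannot be derived from the documents: it is between 0 and 24 of the 25. No statistical result in Section 7 depends on it.

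The placing of the fastest-speed bout before the stress test is a secondary matter to confirm, not a contradiction.

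**What to change.** Reconcile Section 4, procedures 1, 3 and 4 and the Risks text in Section 5, and the able-bodied criteria in Section 6, so that:

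- procedure 3 and Risks name the same participants for the stress test;
- procedure 1 names the cohort to which physician clearance applies, consistently with its session count;
- procedure 4 and Risks agree on whose heart rate is monitored;
- the able-bodied criteria agree with whatever screening applies to people doing that training.

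Alternatively, state that able-bodied people do not do the Cohort 1 training and amend Section 4 to match. The investigators should also confirm that the fastest-speed bout is meant to precede the stress test.

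Which clinical rule applies is for the investigators, and none is proposed here. The cost of the reconciliation is a few sentences of protocol wording; any further cost depends on the rule they choose.
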